Appendix 1 Processing of Missing Dates

Missing dates in combined medications should be imputed as follows:

For the start date, if only the day is missing, the date is defaulted to be the first day of the corresponding month, and if both the month and the day are missing, the date should be imputed as January 01. For the end date, if only the day is missing, the date is defaulted to be the last day of the corresponding month, and if both the month and the day are missing, the date should be imputed as December 31. The imputed start date should be earlier than the end date.

Missing dates for adverse events (AEs) should be imputed as follows:

1) If the AE end date is missing

- If the year and month are known, the last day of the known month should be used for imputation.
- If only the year is known, “December 31” should be used for imputation.
- For AEs leading to death, the AE end date should be the date of death or the imputed end date, whichever is earlier.
- Dates in other situations are considered as missing.

2) If the AE start date is missing

- If the year and month are known and earlier than the year and month of the first dose of the investigational drug, the last day of the known month should be used for imputation.
- If the year and month are known and equal to the year and month of the first dose of the investigational drug, the AE start date should be equal to the date of the first dose of the investigational drug (date refers to “XX month XX day”).
- If the year and month are known and later than the year and month of the first dose of the investigational drug, the first day of the known month should be used for imputation.
- If the year and month are known and the year is earlier than the year of the first dose of the investigational drug, “December 31” should be used for imputation.
- If only the year is known and equal to the year of the first dose of the investigational drug, the AE start date should be equal to the date of the first dose of the investigational drug (date refers to “XX month XX day”).
- If only the year is known and later than the year of the first dose of the investigational drug, “January 01” should be used for imputation.

- If the year, month, and day are all missing, the date of the first dose of the investigational drug should be used as the corresponding start date.
- If the imputed start date is later than the end date, the end date should be used as the corresponding start date.
- Dates in other situations are considered as missing.

If the date of death is incomplete:

- In the safety analysis, the death record needs to be included, and the missing date of death will not be imputed.
- In the efficacy analyses, if the year and month of the date of death are known, the first day of the month should be used for imputation. Otherwise, the date of death will not be imputed, and the death record will be censored for the calculation of time-event indicators (such as OS).

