3.6 EFFICACY ANALYSIS

The analysis will be performed based on the safety analysis set.

The investigator will perform efficacy assessments according to the Response Evaluation Criteria in Solid Tumors Version 1.1 (RECIST v1.1).

Objective Response (ORR): The number and proportion of subjects who achieve objective tumor response (CR or PR) will be summarized. Objective response rate will be determined along with 95% confidence interval. (Clopper-Pearson method).

Progression Free Survival (PFS): PFS is defined as the time from the date of first study dose to disease progression or death (whichever occurs first). Subjects without event (no disease progression or death) will be censored at the date of “last tumor assessment”. Kaplan-Meier methodology will be used to estimate median PFS, PFS rate at various time points, and their 95% confidence intervals. Kaplan-Meier curves will be constructed to provide a visual description of the PFS change with time.

Duration of response (DOR): Duration of response (complete response or partial response) for responders is defined as the time interval between the date of the earliest qualifying response and the date of PD or death for any cause (whichever occurs earlier). For subjects who do not have progressive disease following the qualifying response, duration of response will be censored on the date of last evaluable tumor assessment. Subjects without tumor assessment records after the earliest date of qualifying response will be censored on the earliest date of qualifying response. The analysis method is the same as that of PFS.

Time to Progression (TTP): TTP is defined as the time from the date of first study dose to disease progression. Subjects without event (no disease progression) will be censored at the date of “last tumor assessment”. The analysis method is the same as that of PFS.

Disease Control Rate: Disease control rate (DCR) is defined as the proportion of subjects who achieve CR, PR, and SD based on RECIST v1.1. The disease control rate and its 95% confidence interval (Clopper-Pearson method) will be calculated.

Overall Survival (OS): Overall survival is defined as the time interval between the date of the first investigational product dose to the date of death from any cause. Subjects who are still alive at the analysis cutoff date will be censored at the date of the last known survival. The analysis method is the same as that of PFS.

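### Deaths with an unknown month are censored in OS, against the SAP's own OS definition, and first-of-month imputation of death dates has no lower bound

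*SAP*

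**What the plan says.** The rules are in the SAP appendix on processing of missing dates (Appendix 3 in the contents and in SAP 3.9, but headed Appendix 1). For an incomplete date of death they give three instructions:

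- Safety: "In the safety analysis, the death record needs to be included, and the missing date of death will not be imputed".
- Efficacy, day missing: "if the year and month of the date of death are known, the first day of the month should be used for imputation".
- Efficacy, anything less complete (year only, or no date): no imputation, and "the death record will be censored for the calculation of time-event indicators (such as OS".

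SAP 3.6 defines the endpoints that use these dates. "Overall survival is defined as the time interval between the date of the first investigational product dose to the date of death from any cause". Its only OS censoring rule is: "Subjects who are still alive at the analysis cutoff date will be censored at the date of the last known survival". PFS also has death as an event: "PFS is defined as the time from the date of first study dose to disease progression or death (whichever occurs first". DOR ends at progression or death; TTP ends at progression only.

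Protocol 10.4 has no rule for partial dates. SAP 3.9 sends the reader to section 3.5 for efficacy censoring, but 3.5 is the safety section; the censoring text is in 3.6.

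**The concern.** A death with no known month is still a confirmed event. Censoring it removes an event while leaving the subject's exposure in the analysis, so the estimated hazard falls and the survival curve rises. The censoring is also informative, because it is applied only to subjects who have died. The same subject would appear as dead in the safety tables and as censored on the OS curve. The SAP does not say on which date such a record is censored, so two programmers could produce different results.

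The day-missing rule has a separate defect. Nothing requires the imputed date to fall on or after the first dose, the last tumor assessment or the last known-alive date. A subject seen alive on the 20th could be dated as dead on the 1st, and a death in the month of first dose could give a negative survival time. The same appendix does apply order checks to imputed medication and adverse event dates.

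The trial is single-arm, with about 40 subjects planned for Phase II, so there is no control arm in which the same error could offset.

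**Working it through.** The plan gives no figure tied to this rule, so there is nothing to reproduce. I checked the text first and then sized the effect under stated assumptions.

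**Text.** OS in SAP 3.6 ends at death and censors only the living. The appendix censors a group that is, by definition, not living. Neither passage defers to the other, and no other passage resolves the conflict.

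**Inputs.**
- Median OS of 6.5, 10.7 and 13.6 months: arms of published trials cited in Protocol 2.2. They are background, not design assumptions.
- Survival contact every 12 weeks (84 days): Protocol 7.5.4.
- My assumptions: exponential survival; administrative censoring uniform over 12 to 30 months; last known alive uniform over 0 to 84 days before death; incomplete dates unrelated to survival time; 5%, 10% or 20% of deaths without a month; 10% or 20% without the day. The documents give no rate of incomplete dates.

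**Limb 1: deaths censored.** If a share p of deaths is lost as events, the hazard is multiplied by about (1 − p) and the median by 1/(1 − p): 1/0.95 = 1.053, 1/0.90 = 1.111, 1/0.80 = 1.25. A Kaplan-Meier simulation (400,000 subjects per scenario), with these deaths censored at last known alive, gave these medians in months:

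| Share without month | Complete dates | SAP rule | Ratio |
|---|---|---|---|
| 5% | 6.49 / 10.69 / 13.61 | 6.78 / 11.22 / 14.28 | 1.045 / 1.050 / 1.049 |
| 10% | 6.49 / 10.74 / 13.54 | 7.13 / 11.81 / 14.92 | 1.099 / 1.100 / 1.102 |
| 20% | 6.51 / 10.73 / 13.62 | 7.92 / 13.18 / 16.82 | 1.217 / 1.228 / 1.235 |

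The ratios fall a little below 1/(1 − p) because censoring precedes the true death by up to 84 days. A separate simulation of 3,000 trials of 40 subjects, with an exponential estimate and follow-up of 18 to 30 months, agrees. For a true median of 10 months it gave 10.09 / 10.63 / 11.16 at 0 / 5 / 10% (increases of 5.4% and 10.6%). For 14 months it gave 14.20 / 14.94 / 15.89 (5.2% and 11.9%).

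**Limb 2: first of the month.** The shift is at most 30 days and averages (30.44 − 1)/2 = 14.7 days, or 14.7/30.44 = 0.48 month per affected death. If 20% of deaths lack the day, the expected shift in the median is 0.20 × 0.48 ≈ 0.10 month downward. The simulation agrees: 6.49 to 6.40, 10.71 to 10.61, and 13.59 to 13.49. About 21 to 23% of these deaths were dated before the last known-alive date, and about 4 to 6% had a negative OS time.

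**With the correction** (every known death an event; undated deaths at last known alive + 1 day; first-of-month dates floored at the same day):

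| Scenario | Complete dates | Corrected | Difference |
|---|---|---|---|
| 10% without month | 6.49 / 10.74 / 13.54 | 6.37 / 10.61 / 13.43 | −0.12 / −0.13 / −0.11 |
| 20% without month | 6.51 / 10.73 / 13.62 | 6.27 / 10.48 / 13.39 | −0.24 / −0.25 / −0.23 |
| 20% without day | 6.49 / 10.71 / 13.59 | 6.41 / 10.62 / 13.50 | −0.08 / −0.09 / −0.09 |

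The floor moves the median by only 0.01 month relative to the SAP rule. Its value is that it removes impossible dates.

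**The case against.** The strongest reply is that such records should be rare. Protocol 8.4.4 collects the date of death for SAEs, 8.5.1 requires SAE reports within 24 hours, 8.4.7 makes death from progression an expedited SAE, and 9.2 has missing data queried. Contacts every 12 weeks normally bracket a death. This stands as a limit on likely size. It does not remove the problem: under 8.4.3, active reporting of new events is no longer required after safety follow-up, and later deaths are learned of mainly through the survival contacts.

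The effect is also small against sampling error. With 40 subjects, a 10-month median and follow-up of 18 to 30 months, about 32 deaths are expected, so 5% is one or two subjects and 10% about three. The standard error of an exponential median is about 10/√32 = 1.8 months, so the 0.5-month shift at 5% is about 0.3 standard errors. That is fair, but the shift is systematic, favourable and avoidable.

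A reader might infer three stronger things that the documents do not support:

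- That the survival results are biased. No rate of incomplete dates is given, and with complete dates there is no bias.
- That OS, PFS and DOR are all inflated alike. PFS and DOR are not named in the rule; they are reached because OS is only its example and death is one of their events. They change only if death comes before documented progression, and scans continue after treatment stops for other reasons (Protocol 5.6.2). Only OS was simulated.
- That the two defects compound. They run in opposite directions.

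**Conclusion.** The point holds for OS as a defect in the rule as written: it censors confirmed deaths, against SAP 3.6 and against the safety analysis. If 5%, 10% or 20% of deaths lack a month, median OS is overstated by about 5%, 10 to 11% or 22 to 24%. These shares are assumptions; the percentages depend little on the median assumed. PFS and DOR are affected only for deaths that precede documented progression; TTP is not affected.

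The missing floor on first-of-month dates is a lesser, separate defect. It acts downward, by at most 30 days per affected death and about 0.1 month on the median if 20% lack the day.

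OS, PFS and DOR are secondary endpoints, no survival hypothesis is tested, and the primary ORR and the response-count criteria do not use death dates. DOR is only one of several endpoints weighed, without binding force, when the response count falls in the evaluate range. This should be corrected, but no primary conclusion depends on it.

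**What to change.** Replace the efficacy paragraph on incomplete death dates with one rule. Every known death is an event for OS, and for PFS and DOR where it precedes documented progression. Its date is:

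- month and year known: the later of the first day of that month and the day after the last known-alive date;
- year only: the later of 1 January of that year and the day after the last known-alive date;
- no date: the day after the last known-alive date.

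Count the first dose as a known-alive date, so that no survival time is negative. State in the SAP that the rule takes the earliest admissible date and is therefore slightly conservative: about 0.1 month on the median if 10% of deaths lack a month, and 0.2 to 0.25 month at 20%. Report how many death dates were imputed, and by which line of the rule. In the same edit, correct the appendix number and point SAP 3.9 to section 3.6.

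The cost is one paragraph and a few lines of code, with no new data. Survival estimates may come out slightly less favourable. The change is best made before database lock, so that it is not a choice made with the results in view.
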